10. DATA ANALYSIS

a. Quantitative

i. Sample size and statistical power

Due to low accrual rates the sample size has been revised down.

Sample Size: It is anticipated that 5 patients will be recruited per week and expect a 20% drop-out for assessment of the primary endpoint, HbA1c at 6 weeks post randomization. Patients will be randomized equally between the four intervention groups (three experimental and standard of care control), two of which will be dropped at the interim analysis. As such with N=198 randomized equally (ie 33 in each arm at each stage) there is 90% power to detect a difference in means equivalent to effect size of 0.6 SD between the best performing experimental arm and control using a t-test in the final analysis (1-sided alpha=0.10).

It is not possible at this stage to determine the number of Aboriginal and Torres Strait Islanders (ATSI) patients included.

ii. Statistical methods

We will implement a two-stage drop-the-loser design initially comparing three experimental interventions against control. The first stage requires 132 patients at which the two worse performing experimental interventions will be dropped. The difference in means with control arm as common reference are assumed multivariate normally distributed allowing for control of the type I error rate.³⁸ Being an early phase trial focusing on proof-of-concept evidence of intervention efficacy, we set the type I error rate to be 10% (one-sided), while maintaining a small type II error rate.

iii. Secondary Analysis: Bayesian

As a secondary analysis of the primary outcomes will consist of a Bayesian analysis .both at the interim and final assessments. An empirical prior distribution for the difference in means is constructed from diabetes studies registered on ClinicalTrials.org reporting HbA1c as the primary outcome. In particular the search criteria were: (i) completed (ii) phase 3 (iii) supremacy (iv) interventional (v) randomized (vi) controlled trials (vii) in adults (viii) with diabetes (ix) reporting data allowing the calculation of group mean differences for HbA1c (% units as opposed to mg/dL) (x) assessed within 7 months post randomization. For HbA1c, only studies reporting percentage units (as opposed to mg/dL) were included. When multiple assessments were reported per study only the earliest (post randomization) are included the analyses. For assessment of the between study variance, when multiple experimental (or comparator) groups are reported at an assessment these are merged with the total experimental (or comparator) group means and variances estimates calculated accordingly. For the multivariate joint prior at the interim analysis a between arm correlation of 0.5 is assumed due to equal randomized allocations and assumed equal within group variances at each assessment. Random-effects meta-analyses were performed to estimate the between study variance and thereby the total variance in the treatment effects using restricted maximum likelihood estimation (metafor R package).

We identified 257 studies reporting group mean differences for HbA1c (% units) as the primary outcome assessed a median 24 weeks (interquartile range=[24, 26]) post randomization. The random effects meta-analyses estimated weighted mean of differences between experimental and comparator groups in HbA1c was -0.50%, with a between study variance (SD) of 0.13 (0.36) representing $I^2=94%$ of the total variance.

We set the joint prior distribution for the Bayesian analyses to be bivariate Gaussian normal with mean zero, marginal variances (as estimated above) and the between group correlations to be $\rho=0.5$ at the interim analysis (see Figure 1). At each assessment we calculate both the joint and marginal posterior probabilities of the group mean difference between experimental and control arms lying being lower than 0 (ie positive treatment effect) and/or lower than 0.3% (a commonly used minimal clinically interesting difference for HbA1c).

[figure not shown]

Figure 1: (A) Density distribution of observed study results (grey), and Gaussian distributions with estimated between-study mean differences (blue) and the same distribution centered at zero difference (skeptical prior); and (B) the contour plot of the Bayesian joint prior distribution of treatment effects for the interim analysis. The dashed lines indicate differences of ± 0.3 .

b. Qualitative

N/A

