coordinator, [name]) requesting an appointment to visit the patient's home to collect the blood sample. At the home visit the study coordinator will also present some information about other clinical trials that maybe of interest to the patient. However, the patient is under no obligation to participate. y. In the event that the patient cannot be contacted by phone we will write to them and include an accompanying Diabetes Distress Scale questionnaire and a reply-paid envelope.

Based on the 6-week HbA1C results, the 2 study groups from 2, 3 and 4 with the least change in HbA1C from baseline will no longer be followed (called 'drop the loser') with the remaining study group left to compare with study group 1.

The HbA1C and triglyceride blood test at 6 weeks is part of normal routine practice and therefore billed to Medicare.

c. Access to Existing Data

Patient medical records including enrolled patient's HbA1C and triglyceride blood tests.

d. Data Linkage Management

Data linkage methods will be required to link enrolled patient blood test results and admission data to readmission and length of study data from the SA Health Integrated South Australian Activity Collection (ISAAC. This is of interest in the 12-month period following the patients index admission and subject to further funding.

i) Privacy and Confidentiality

- A random unique patient identifier will be created and appended to the linked data file
- The following potentially identifying data items will be dropped:
 - o Medicare Number/IRN
 - o Date of birth (replaced with the calculated field age)
 - o Hospital URN
 - o Separation date/time and admission date/time (replaced by length of stay hours)

ii) During the Project

The research and questionnaire data of participants will be recorded in an Adelaide University REDCap (Research Electronic Data Capture) database, identified by a unique study number only. Participant identifying information will be recorded on a separate spreadsheet and stored on a password protected computer, accessible only to study staff for the 6-week follow-up visit.

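### The retained arm's effect will be overstated by up to about 0.08 SD if it is reported as a plain difference pooled over both stages; a selection-adjusted estimate should stand beside it

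*Protocol*

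**What the plan says.** Protocol section 10.a.i plans "N=198 randomized equally (ie 33 in each arm at each stage") and claims that "there is 90% power to detect a difference in means equivalent to effect size of 0.6 SD". The comparison is "between the best performing experimental arm and control using a t-test in the final analysis (1-sided alpha=0.10"). Drop-out for the primary endpoint is put at 20%.

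Section 10.a.ii adds that "The first stage requires 132 patients at which the two worse performing experimental interventions will be dropped". On error control, "we set the type I error rate to be 10% (one-sided"), with control resting on the joint multivariate-normal distribution of the differences from the common control.

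Section 9.b gives the selection rule: "the 2 study groups from 2, 3 and 4 with the least change in HbA1C from baseline will no longer be followed", "with the remaining study group left to compare with study group 1". Section 8 names the primary outcome as HbA1c at 6 weeks.

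The protocol does not say in words whether stage-1 patients count in the final comparison, and it names no estimator for the size of the retained arm's effect.

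**The concern.** The arm that goes forward is the one whose stage-1 result looked best, partly because it is better and partly by chance. If its stage-1 patients are pooled with its stage-2 patients, half of its mean carries that favourable chance. A boundary set from the joint distribution of the differences allows for this in the test, but it does not move the estimate.

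The overstatement is largest when the arms are similar, which is plausible here. Groups 2, 3 and 4 all receive the self-care, coping and sleep sheets. Groups 3 and 4 also share the whole-foods sheet and differ only in the activity sheet (section 9.b). The introduction describes a pilot meant to establish which intervention, if any, is most effective, so readers will look at the size of the winner's effect as well as its p-value.

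**Working it through.** **Inputs.** From section 10.a: 33 randomised per arm per stage, that is 4 × 33 = 132 in stage 1 and 2 × 33 = 66 in stage 2, total 198; 20% drop-out, so 33 × 0.8 = 26.4 evaluable per arm per stage and 52.8 per retained arm; one-sided alpha 0.10; effect 0.6 SD; one of three experimental arms kept. The within-arm SD of HbA1c is not given. The 0.36 in section 10.a.iii is a between-study SD and cannot stand in for it.

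**Step 1: the stated 90% power.** The two-stage design was simulated (1,000,000 trials): select the best of three, then test the retained arm against control. The boundary was set to give 10% one-sided error when no arm works.

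| Reading | Power at 0.6 SD |
|---|---|
| Both stages pooled, 26.4 per arm per stage, adjusted boundary z = 1.63, effects 0.6/0/0 | 90.7% (select best arm and reject); 91.3% (any rejection) |
| Pooled, 52.8 per arm, single t-test, unadjusted | 96.3% |
| Pooled, 66 per arm, single t-test, unadjusted | 98.4% |
| Pooled, 33 per arm per stage, adjusted boundary | 95.3% |
| Stage 2 only, 33 per arm, t-test | 87.3% |
| Stage 2 only, 26.4 per arm, select and reject | 79.3% |

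The first row matches the stated figure. A Bonferroni level of 0.10/3 with 52.8 per arm gives 89.4%, and that reading pools the stages too. The stage-2-only readings fall short. An unadjusted boundary of 1.28 would also give about 18% type I error under the global null. The stated power therefore points to pooled data and an adjusted boundary.

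**Step 2: bias of the pooled difference.** With three equally effective arms, the selected arm's stage-1 mean is too favourable by E[max of 3 standard normals] × SD/√n, where E[max] = 0.846. Stage 1 is half of the pooled mean and the control mean is not selected, so

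bias = ½ × 0.846 × SD/√n.

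- n = 33: ½ × 0.846/5.745 = 0.074 SD
- n = 26.4: ½ × 0.846/5.138 = 0.082 SD

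Simulation gives the same values and shows how the bias falls as the arms separate:

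| True effects (SD) | Bias, n = 26.4 | Bias, n = 33 |
|---|---|---|
| all equal | 0.082 | 0.074 |
| 0.2/0.4/0.6 | 0.052 | 0.042 |
| 0.6/0.3/0.3 | 0.050 | 0.039 |
| 0.6/0/0 | 0.009 | 0.005 |

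For scale, the nominal standard error of the pooled difference is √(2/52.8) = 0.195 SD, so the maximum bias is 0.082/0.195 = 0.42 of a standard error. Against the design effect it is 0.082/0.6 = 14%.

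**Step 3: HbA1c units.** Assumed SD 0.5%, 1%, 1.5%, 2%: 0.082 × SD = 0.04%, 0.08%, 0.12%, 0.16%.

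**Step 4: if selection and final test use different measures.** Section 9.b selects on change from baseline; section 8 names the 6-week value. Suppose the final test uses the 6-week value, with equal variances and an assumed baseline correlation of 0.5. The change then has SD √(2 − 2 × 0.5) = 1 and correlation 1 − 0.5 = 0.5 with the 6-week value, so the bias roughly halves.

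**Step 5: the adjusted estimator** (two-stage conditionally unbiased estimate for the selected arm minus the control mean), in SD units with 26.4 per arm per stage:

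| True effects | Pooled: bias / SD / RMSE | Adjusted: bias / SD / RMSE |
|---|---|---|
| all equal | 0.082 / 0.184 / 0.201 | 0.000 / 0.216 / 0.216 |
| 0.2/0.4/0.6 | 0.052 / 0.190 / 0.197 | 0.000 / 0.209 / 0.209 |
| 0.6/0/0 | 0.009 / 0.195 / 0.195 | 0.000 / 0.198 / 0.198 |

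Stage 2 alone is also free of selection bias, but its standard error is √(2/26.4) = 0.275.

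**The case against.** The strongest reply is that the protocol names no point estimate, and that the choice of estimator after selection commonly belongs in an analysis plan, which is not shown here. The sentence about the t-test is a power statement. This stands in part: one cannot say that the trial will report a biased effect, only that a plain pooled difference would be biased and that the protocol states no correction. What the protocol does fix is the design, the comparison and, through its power figure, the reuse of stage-1 data.

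A reader might infer that the bias is a sizeable share of the 0.3% difference that section 10.a.iii calls "a commonly used minimal clinically interesting difference for HbA1c", and that the primary estimate will be judged against it. The documents do not support that. The share needs an HbA1c SD that they do not give. The 0.3% appears only in the secondary Bayesian analysis, whose zero-centred prior already shrinks the estimate. With prior variance 0.13 and sampling variance 2 × SD²/52.8, the posterior mean keeps 0.13/(0.13 + 0.038) = 77% of the observed difference at SD 1.0%, 60% at 1.5% and 46% at 2.0%. Nor does the protocol say that this estimate will size a later trial.

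A reader might also infer that the test is invalid. It is not: the protocol plans type I error control, and the reproduced power fits an adjusted boundary.

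Finally, the conditionally unbiased estimator has the higher RMSE in every scenario above. Making it the sole reported effect would trade accuracy for unbiasedness, so that would be a preference and not a correction.

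**Conclusion.** The point holds in a limited form. The test is sound as planned. A plain pooled difference for the retained arm is selection-biased in favour of the intervention, by at most 0.074 to 0.082 SD, and the protocol's type I error control does not remove this. The maximum needs three equally effective arms, the same HbA1c measure for selection and final comparison, and pooling of both stages, which is inferred from the stated power. With graded effects of 0.2/0.4/0.6 SD the bias is about 0.04 to 0.05 SD; with one clearly best arm it is under 0.01 SD. Conversion to HbA1c percentage points rests on an assumed SD. This is a worthwhile, inexpensive improvement to how the winner's effect is reported, not a fault that threatens the trial's conclusion on efficacy.

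**What to change.** Keep the drop-the-loser test unchanged. In section 10.a:

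1. State that stage-1 data from the retained arm and control enter the final comparison, and on which HbA1c measure.
2. Report a selection-adjusted estimate beside the pooled difference, for example the two-stage conditionally unbiased estimator for the selected arm minus the control mean.
3. Note that the pooled difference is selection-biased wherever the size of the retained arm's effect is interpreted.

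The cost is a few lines of text and code, with no new data and no change to sample size or error rate. The drawback is the larger variability of the adjusted estimate (SD 0.216 against 0.184 with equal arms), which is why both estimates should be shown.

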8. STUDY OUTCOMES

a. Quantitative

i. Primary Outcome

- Improved blood sugar control measured by HbA1C at 6 weeks

ii. Secondary Outcome(s)

- a. Change in triglyceride and diabetes distress at 6 weeks
- b. Reduction in readmission to hospital or if re-admitted, a reduction in length of stay
- c. Relationship of psychosocial, environmental and health related factors to the effect of the intervention.

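### The only final HbA1c test named is a t-test without baseline adjustment; ANCOVA on baseline HbA1c at both stages would gain precision and align selection with testing

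*Protocol*

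**What the plan says.** Protocol section 8 gives the primary outcome as "Improved blood sugar control measured by HbA1C at 6 weeks". Section 10.a.i states that "there is 90% power to detect a difference in means equivalent to effect size of 0.6 SD" between the best experimental arm and control, "using a t-test in the final analysis", with "1-sided alpha=0.10". The size is "N=198 randomized equally (ie 33 in each arm at each stage", and the investigators "expect a 20% drop-out for assessment of the primary endpoint". Section 10.a.ii describes the two-stage design in terms of differences in means against a common control, treated as multivariate normal. Neither the frequentist section nor the Bayesian section (10.a.iii) mentions a covariate.

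The six-week follow-up text in section 9.b selects arms differently: the two experimental groups "with the least change in HbA1C from baseline" are dropped. Section 9.c lists access to patients' "HbA1C and triglyceride blood tests" in the medical records. It gives no date window for the baseline value and does not say how complete it will be.

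**The concern.** Section 7 sets no HbA1c limits for entry, so a wide baseline spread can be expected. The self-care sheet in Appendix 3 describes HbA1c as an average over about three months, so a value taken at six weeks partly reflects the time before randomisation. Some correlation between the baseline and 6-week values is therefore likely, and a comparison that leaves baseline out carries variance that could be removed without extra patients.

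Consistency is also at stake. Arms are selected on a change from baseline, while the final test is described as a difference in means on an outcome named simply as HbA1c at six weeks. If selection and testing use different statistics, the critical value that holds the error at 10% depends on a correlation that the protocol does not state. Efficiency matters because section 10.a.i says the sample size was reduced for slow accrual.

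**Working it through.** **Inputs from the protocol.** N = 198 with 33 per arm per stage (4 × 33 + 2 × 33 = 198), so 66 per final arm. With 20% drop-out, 66 × 0.8 = 52.8 are evaluable per final arm, or 26.4 per arm per stage. One-sided alpha is 0.10, the effect 0.6 SD and the stated power 90%.

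**Assumptions.** The correlation r between baseline and 6-week HbA1c is not given; 0.3 to 0.8 is shown. SDs are taken as equal at both times. One experimental arm has the effect and the other two have none.

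**Step 1: reproduce the stated power.** The design was simulated with known variance: keep the best of three experimental arms after stage 1, pool the stages, and set the critical value for 10% one-sided error when no arm works. The critical value is z = 1.633. At 0.6 SD the probability of keeping the right arm and rejecting is 90.7% (91.3% for any rejection). The stated 90% thus already allows for drop-out and selection, and it holds with no baseline gain. A plain two-arm calculation with 52.8 per arm gives 96.4%, and the simulation without drop-out gives 95.4%, so neither is the source of the 90%.

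**Step 2: t-test on the 6-week value.** ANCOVA multiplies the variance by 1 - r². The effect detectable with the stated power becomes 0.6 × √(1 - r²). The equivalent number of unadjusted patients per final arm is 52.8/(1 - r²).

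| r | Variance saving | Detectable effect (SD) | Equivalent n per arm | Power at 0.6 SD | Power at 0.4 SD |
|---|---|---|---|---|---|
| no adjustment | – | 0.60 | 52.8 | 90.7% | 61% |
| 0.3 | 9% | 0.57 | 58 | 92.9% | 65% |
| 0.5 | 25% | 0.52 | 70 | 96.4% | 73% |
| 0.7 | 49% | 0.43 | 104 | 99.4% | 87% |
| 0.8 | 64% | 0.36 | 147 | 99.95% | 95% |

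The 0.4 SD column is illustrative; the protocol does not target that effect.

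**Step 3: t-test on change from baseline.** A change score has variance 2(1 - r) relative to the 6-week value. The ratio of ANCOVA to change is (1 - r²)/[2(1 - r)] = (1 + r)/2, so the saving is (1 - r)/2: 35% at r = 0.3, 25% at 0.5, 15% at 0.7 and 10% at 0.8. If 0.6 SD is read in units of the SD of change, the detectable effect is 0.6 × √((1 + r)/2) = 0.48, 0.52, 0.55 and 0.57 SD. Here the gain shrinks as r rises, the reverse of Step 2.

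**Step 4: different statistics at the two stages.** If arms are selected on change but tested on the 6-week value, the critical value for exactly 10% error falls from 1.633 to about 1.48 at r = 0.5 and 1.41 at r = 0.8. Keeping 1.633 would then be conservative, by an amount that depends on the unstated r.

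**The case against.** The t-test appears in the power sentence. Section 10.a.ii, which describes the methods, speaks only of differences in means, and that wording would also fit adjusted differences. Powering on a simple t-test and naming covariates in a statistical analysis plan is common, and a plan may exist that is not shown. The document's only account of how arms are compared on HbA1c is the change-from-baseline rule, so the final test may also be on change. No correlation is given, and because baseline values come from records without a date window, a low r cannot be excluded.

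Most of this stands as a limit on the point. A reader might infer that the final test certainly ignores baseline, that much of the trial's information is wasted, or that the trial is underpowered. The documents support none of these: the input to the t-test is not stated, r is unknown, and the stated power reproduces at the protocol's own effect size. The fall to 61% at 0.4 SD is not a defect of the stated design either. A reader might also assume that every patient has an HbA1c from the index admission, or that adding hospital as a covariate would help; the protocol shows neither.

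The objection does not remove the recommendation. The protocol names a specific final test and a selection rule expressed in a different statistic, and ANCOVA has the lower variance under either reading of the t-test for every r considered.

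**Conclusion.** The point holds as a recommendation on efficiency and consistency. The named analysis is valid and achieves its stated power, so nothing is wrong in the sense of bias or inadequate size. ANCOVA would save 9% to 64% of the variance against a t-test on the 6-week value, or 35% to 10% against a t-test on change, as r goes from 0.3 to 0.8. At r = 0.5 both readings give 25%, and power at 0.6 SD goes from about 91% to about 96%. These sizes rest on the assumed r, equal SDs at the two times, a usable baseline value for nearly all patients, and the 20% drop-out stated in the protocol. Using one estimator at both stages also makes the critical value independent of r.

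**What to change.** In section 10.a, name the primary estimator at both the interim selection and the final analysis: an ANCOVA of 6-week HbA1c on study group with baseline HbA1c as covariate. Reword the selection rule in section 9.b so that arms are ranked on that adjusted difference from control, and derive the critical value for the same statistic. Keep the t-test as a sensitivity analysis, stating whether it uses the 6-week value or the change. Define baseline HbA1c as the pre-randomisation value in the records within a stated window. Keep patients who have no such value by imputing the mean of the covariate.

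The cost is a few sentences, one degree of freedom, and abstraction of the baseline value for every patient. No extra patients or visits are needed.

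### The secondary Bayesian analysis prints its clinical-relevance threshold for HbA1c without a minus sign, so the criterion is weaker than any benefit at all

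*Protocol*

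**What the plan says.** Section 10.a.iii of the Protocol plans a Bayesian analysis of HbA1c at the interim and final assessments, labelled secondary. Three statements there fix the direction of the effect and the prior:

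- Benefit is a group mean difference "lying being lower than 0 (ie positive treatment effect").
- The meta-analysis behind the prior found that the "weighted mean of differences between experimental and comparator groups in HbA1c was -0.50"%, "with a between study variance (SD) of 0.13 (0.36").
- The prior is "bivariate Gaussian normal with mean zero, marginal variances (as estimated above"), with correlation 0.5 at the interim.

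The same sentence that defines benefit then adds a second event: "and/or lower than 0.3% (a commonly used minimal clinically interesting difference for HbA1c"). The legend of the figure showing the prior says "The dashed lines indicate differences of" ±0.3.

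On the number of comparisons, section 10.a.ii states: "We will implement a two-stage drop-the-loser design initially comparing three experimental interventions against control". Two of the three experimental arms are dropped after the first stage.

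**The concern.** With negative values meaning benefit, a clinically interesting benefit must be a difference below -0.3. The printed condition, below +0.3, is easier to meet than the condition below 0 that precedes it. The connecting and/or does not rescue it: below 0 and below 0.3 is simply below 0, while below 0 or below 0.3 is simply below 0.3. Neither combination isolates an effect of at least the stated minimal size.

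What is at stake is how a secondary result is read. The trial is a proof-of-concept study with a one-sided 10% type I error, and these probabilities are the only quantities in the analysis section tied to clinical relevance. Coded literally, they would attach a large probability to a supposedly clinically interesting effect in a trial that found no difference. Changing the sign once results are known would look like a post hoc change.

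The word bivariate raises a smaller, unrelated question, because neither stage has two comparisons with control: there are three at the interim and one at the end.

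**Working it through.** **Inputs from the Protocol.** Prior mean 0 and variance 0.13 (10.a.iii); 33 patients per arm per stage and 20% drop-out (10.a.i).

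**Input assumed.** The HbA1c standard deviation (SD) is not given. I use 1.0, 1.5 and 2.0 percentage points.

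**Reproducing the plan's figures.** √0.13 = 0.361, which matches the stated 0.36. Sample size: 4 × 33 + 2 × 33 = 198, as stated. Evaluable patients per retained arm at the end: 66 × 0.8 = 52.8, taken as 53.

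**Prior alone.** 0.3/0.361 = 0.832, so P(difference < +0.3) = Φ(0.832) = 0.80 and P(difference < -0.3) = Φ(-0.832) = 0.20. If the intended prior variance is instead the total variance, 0.13/0.94 = 0.138, the values are 0.79 and 0.21.

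**Posterior at the final analysis.** For an observed difference d:

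- sampling variance V = 2 × SD²/n
- posterior variance = 1/(1/0.13 + 1/V)
- posterior mean = w × d, with w = 0.13/(0.13 + V)

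For SD 1.5, n = 53 and d = 0: V = 2 × 2.25/53 = 0.0849. Posterior variance = 1/(7.692 + 11.778) = 0.0514, so the posterior SD is 0.227. Then P(< +0.3) = Φ(0.3/0.227) = 0.907 and P(< -0.3) = 0.093.

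| Assumed SD | Posterior SD | As printed (< +0.3) | Negative threshold (< -0.3) |
|---|---|---|---|
| 1.0 | 0.171 | 0.96 | 0.04 |
| 1.5 | 0.227 | 0.91 | 0.09 |
| 2.0 | 0.264 | 0.87 | 0.13 |

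With no drop-out (66 per arm) the printed rule gives 0.97, 0.92 and 0.89 (0.972, 0.922, 0.885).

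**Averaged over null trials.** An observed difference of exactly zero is one case. When the true difference is zero, the average of P(< +0.3) is Φ(0.3/√(posterior variance + w²V)). For SD 1.5: w = 0.605 and w²V = 0.0311, giving Φ(0.3/√0.0825) = 0.85. For SD 1.0 and 2.0 it is 0.91 and 0.83. This treats the retained arm as fixed and ignores its selection at the interim.

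**Response to other results (n = 53).**

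| Observed difference | As printed, SD 1.0 / 1.5 / 2.0 |
|---|---|
| +0.5 | 0.30 / 0.50 / 0.60 |
| +1.0 | 0.003 / 0.09 / 0.27 |

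For an observed benefit of 0.5 (SD 1.5) the printed rule gives 0.996, and the negative threshold gives 0.50.

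**Dimension of the prior.** With 26 to 33 patients per arm at the interim, SD 1.0 to 2.0 and observed differences of zero, the joint probability that all differences lie below +0.3 is 0.68 to 0.84 for three differences and 0.74 to 0.88 for two. Each arm's marginal posterior is the same in one, two or three dimensions when prior and likelihood both have correlation 0.5 (SD 1.5, 26.4 per arm: posterior SD 0.272 throughout). The dimension therefore changes only the joint interim probabilities.

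**The case against.** The best defence is that the intent can be recovered. The 0.3% is named as a minimal clinically interesting difference, benefit is defined as negative in the same sentence, and the figure legend marks a line at -0.3. A dropped sign, or lower by 0.3%, is the natural reading. That is probably right about intent, but the text is parallel to the condition below 0, and the legend marks both signs, so it does not settle the matter. Loss in text extraction is unlikely, since the -0.50% nearby kept its sign.

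It is also fair that nothing is decided on these probabilities. No posterior cut-off is set for dropping an arm, stopping or claiming success. Arms are dropped on the six-week HbA1c results (sections 9.b and 10.a.ii), and the final comparison is a t-test at one-sided 0.10. This stands, and it limits the severity.

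Three stronger readings are tempting, and the documents do not support them:

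- A reader might infer that the printed probability is high whatever the data show. It is not: it falls to 0.50 at an observed harm of 0.5 and 0.09 at 1.0 (SD 1.5).
- A reader might take about 90% as a fixed property of a null trial, caused by the sign and the bivariate prior together. It comes from the sign alone, needs an assumed SD and an observed difference of zero, and is 0.91 to 0.83 when averaged over null trials.
- A reader might infer that the interim joint posterior cannot be computed for three arms. Section 10.a.iii also calls the prior multivariate, and a common mean, variance and correlation of 0.5 determine the three-arm version directly.

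**Conclusion.** The point holds for the secondary Bayesian analysis only. The printed threshold contradicts the direction of benefit stated in the same sentence, and no planned probability measures a clinically interesting benefit.

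The prior figures, 0.80 against 0.20, follow from the Protocol alone. The posterior figures, 0.96 to 0.87 against 0.04 to 0.13 at an observed difference of zero, rest on an assumed SD of 1.0 to 2.0 percentage points, 53 evaluable patients per arm and a normal likelihood. The gap stays wide throughout that range.

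Primary test, arm selection and type I error are unaffected, so this should be fixed rather than must be fixed. The bivariate wording is a separate minor mismatch with the three-arm interim.

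**What to change.** In section 10.a.iii, change the threshold to: lower than -0.3% (a reduction of more than 0.3 percentage points relative to control).

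Separately, describe the prior as trivariate at the interim, with all pairwise correlations 0.5, and univariate for the retained arm at the final analysis.

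The cost is two wording changes and the matching line of analysis code, made before results are seen. Sample size, data collection and the primary analysis do not change. The reported probabilities of a clinically interesting effect will be lower than under the printed rule.
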